The combined average of 3 steps or the middle one third of the 30 feet walkway will be used for assessment of PTI. The patient will be blinded from when the time the measurements are taken when walking for the measurement. This will be done by walking with the patient and taking a measurement after the patient has become acclimatised on the measured walkway. Acclimatisation will be quantified by the patient being able to walk and talk without the need of balance assistance i.e. hand on the patient's waist. The middle third of the walk will be used to acquire the measurements of PTI (approximately 3 steps of the foot)

7.2.1.2. *Duration of gait analysis*

Approximately 60 minutes will be given per patient visit to allow for technical and practical issues within the gait measuring room. The process for taking the electronic data measurements is estimated to take between 10 and 15minutes for all three devices however the overall practical process will take longer. The participant will then be allowed to complete the short questionnaire needed for the secondary analysis. This will take no longer than an additional 10minutes.

General Safety

Those experiencing hypoglycaemia from their diabetes at time of measurements will need to be addressed for patient safety reasons. Hypoglycaemia is measured or determined by the patient or the symptoms related to hypoglycaemia i.e. shaking, unbalanced walking, speaking incoherently, slow/slurred speech, sweating, feeling hot, disorientated and measured low blood sugars via the patient's blood sugar machine. When any participant has a hypoglycaemic event or becomes unwell the proceedings will be stopped. Hypoglycaemic events are not considered to

Protocol version 1**Evaluating plantar foot pressure in a novel diabetic offloading device****IRAS code 198005**

be caused by the intervention. The researcher will then seek appropriate medical care. The use of the nursing out patient hospital setting where the gait lab is situated will be used as support to any first aid issues. More serious events will be referred as appropriate to the nearest emergency care services. Rearranging the appointment will be offered following recovery.

7.2.1.3. *Data capture*

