10.6. Ongoing information for Research Ethics Committee

Unless otherwise instructed by the REC and the Sponsor, the Investigator must submit to the REC and the Sponsor:

- Information on serious adverse events that are unexpected and related to study procedures (RUSAEs) from the Investigator's site, within 15 calendar days of the research team becoming aware of them.

Protocol version 1**Evaluating plantar foot pressure in a novel diabetic offloading device****IRAS code 198005**

- Expedited safety reports, as soon as possible.
- Annual reports on the progress of the study.
- The NRES Declaration of End of Study form.

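### General Safety rules out in advance that hypoglycaemia is caused by the intervention, and this is not reconciled with the reporting trigger in section 10.6

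*Combined protocol and SAP*

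**What the plan says.** The General Safety paragraph in section 7.2.1.2 covers participants who become hypoglycaemic or unwell at the gait laboratory.

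- **Identification.** Hypoglycaemia may be determined by the patient or from a list of symptoms that includes shaking, unsteady walking, sweating and disorientation. A low reading on the patient's own meter is also mentioned.
- **Handling.** "When any participant has a hypoglycaemic event or becomes unwell the proceedings will be stopped". Medical care is then sought, and "More serious events will be referred as appropriate to the nearest emergency care services". A new appointment is offered after recovery.
- **Causality.** "Hypoglycaemic events are not considered to" (page break) "be caused by the intervention".

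Section 10.6 sets out what goes to the REC and the Sponsor. The first item is "Information on serious adverse events that are unexpected and related to study procedures", due within 15 calendar days of the research team becoming aware. The second is "Expedited safety reports, as soon as possible", with no definition of content. Annual progress reports are also listed.

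**The concern.** Relatedness is normally judged event by event, on timing, circumstances and alternative explanations. Here it is answered beforehand for the one adverse event that the protocol singles out, and the event can be identified from signs that overlap with difficulty walking in the test device. An unsteady or unwell episode in the boot could be labelled hypoglycaemia and, by that label alone, removed from consideration as device-related.

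The protocol also does not say how this sentence fits with the relatedness condition in 10.6. What is at stake is fair attribution of events to a new device in a proof-of-concept study, and whether a serious episode reaches the REC and the Sponsor.

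**Working it through.** No arithmetic applies: the point depends on no rate, margin or sample size, and the plan states no safety figure to reproduce. The check is a comparison of the relevant sections.

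**1. What is the exposure?** Section 6.7 describes a boot with a metal ankle-foot orthosis that immobilises the ankle and carries its inactive battery unit at full weight around the calf. Section 7.2.1.1 gives up to 10 minutes for a walking tour and 30 minutes for getting used to the boot. Section 7.2.1.2 says "Approximately 60 minutes will be given per patient visit", of which 10 to 15 minutes is measurement in the three devices.

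**2. Can boot effects and hypoglycaemia be confused?** Section 7.2.1.1 judges acclimatisation by whether the patient can walk and talk without being steadied, so the protocol itself expects some initial unsteadiness. Unsteady walking is also on the General Safety symptom list. The wording there can be read as not requiring a glucose reading. On that reading the two can be confused, and the advance statement settles the attribution in one direction.

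**3. Do the two rules use the same term?** No. General Safety speaks of *the intervention*; 10.6 speaks of *study procedures*. Section 6.6, which groups products with interventions, and section 6.5.4 on blinding both suggest that *intervention* means the device. The term is not defined for safety purposes.

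**4. What happens to a serious episode brought on by the session?** Under the first item of 10.6:

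| Reading of *intervention* | Judged unexpected | Judged expected |
|---|---|---|
| Boot only | Reportable if judged related to procedures | Not reportable |
| Whole session | Not reportable, because relation is already ruled out | Not reportable |

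The advance statement changes the reporting outcome in one of the four cells: whole-session reading, unexpected event. In the right-hand column it makes no difference. Because General Safety anticipates hypoglycaemia, an investigator could well place an event there. On either reading of *intervention*, attribution to the boot is fixed beforehand.

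**5. Does anything else capture the event?** General Safety gives no recording step. The variables in section 4.1, the assessments in section 7 and the analyses in sections 9.3 and 9.4 contain no adverse event item. The text gives no adverse event definition, causality scale or expectedness reference. Section 9.1 makes one person responsible for collecting, analysing and reporting the data, so no second assessor is named who might offset the sentence.

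**The case against.** A reader might infer that a serious hypoglycaemic episode could never be counted or reported as related, so that related hypoglycaemia would be zero whatever happened. The documents do not support that.

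- **The trigger is different.** An episode brought on by walking or by the length of the visit can be judged related to study procedures under 10.6 without contradicting General Safety.
- **Other routes exist.** Expedited and annual reports are not worded as depending on relatedness. Section 8.2 provides for written notice to the Sponsor and the REC when the Investigator acts to remove a participant from immediate hazard, with no causality condition. That route is confined to medical emergencies.
- **No such count is planned.** Section 3.1 makes completion of data collection the endpoint, and section 9 plans no adverse event summary. No planned safety result can therefore be falsified.

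Three further arguments have force. The sentence concerns hypoglycaemia arising from diabetes and a boot with its battery inactive, so as a prior expectation about the device it is reasonable. The absence of adverse event recording is general and does not stem from this sentence; section 8.3.1 also refers to CRF Instructions that are not in the documents and may cover it. And deleting the sentence would not settle whether hypoglycaemia counts as unexpected.

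All of this limits the point. It does not remove it: a reasonable prior expectation is not a substitute for assessing each event, particularly when symptoms alone may identify it.

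**Conclusion.** The point holds in a limited form. The protocol prejudges device causality for hypoglycaemia and leaves that judgement unreconciled with 10.6. Misattribution away from the boot is possible on any reading of *intervention*. Under-reporting of a serious episode because of this sentence requires the whole-session reading and an event otherwise regarded as unexpected.

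The conclusion rests on two assumptions: that symptoms can identify hypoglycaemia without a glucose reading, and that the unseen CRF Instructions do not already require case-by-case attribution. The consequence is confined to safety attribution and reporting in a single-visit study of up to 36 participants. The documents give no basis for putting a number on it, and the comparison of pressure time integral is unaffected.

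**What to change.** Remove the advance causality statement from General Safety. In its place, require that each hypoglycaemic or unwell episode during the visit be recorded on the CRF with:

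- its seriousness;
- its expectedness, so that the second condition of 10.6 is decided openly;
- a case-by-case judgement of relation to the device;
- a separate judgement of relation to study procedures.

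Then apply 10.6 to that record. The CRF line is as necessary as the deletion, because at present nothing in the text requires the episode to be written down. No change is proposed to how an episode is managed, to when the session is stopped or to referral. The cost is one sentence and one CRF line.

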8.3.2. Database entry and reconciliation

Case report forms and all electronic data will be entered/loaded in a password protected information technology platform internally secured by Leeds Teaching Hospitals and University of Leeds information technology infrastructure. This is on the NHS Leeds Teaching Hospitals F Drive which is a secured server only accessible by named individuals and password protected. The University of Leeds data will be stored on named individual password protected accounts on the secure server, M Drive. Regular backups of the electronic data will be performed after each entry on the secure One Drive at University of Leeds at [name]

8.3.3. Screening and enrolment logs

Subject's Screening will be recorded in the Subject Screening Log.

The Investigator will keep a list containing all subjects screened and enrolled into the study. This list remains with the Investigator and is used for unambiguous identification of each subject. Subject's Screening will be recorded in the Participant Log Entry. The researcher will keep a list containing all subjects screened and enrolled into the study. This is the anonymised case report file. This is in addition to the Participant Name Study Identity Log. The list contains the subject identification number which links to the full name, date of birth and National Health Security number of each participant. This will be held in a separate password protected data sheet and folder within the infrastructure detailed in 8.3.2.

The subject's consent and enrolment in the study will be recorded in the subject's medical record. These data should identify the study and document the dates of the subject's participation.

8.4. Archiving and data retention

Although not required by law for non-CTIMPs, in line with the principles of ICH GCP essential study documents will be retained for a minimum of 5 years following the completion of the study. For the purpose of a need for 5 year access this will be within the Principle Investigator's Leeds Teaching Hospitals NHS Trust F Drive not the University Of Leeds M Drive due to the Principle Investigators student role terminating in September 2017. The study will be removed from any university data storage and transferred to the Principle Investigator's NHS secured M drive via secure transfer, i.e. encrypted USB device or secure e-mail with password protected documents. Arrangements for confidential destruction will then be made. If a patient withdraws consent for their data to be used, it will be confidentially destroyed immediately. No records/study documentation/data may be destroyed without first obtaining written permission from the Sponsor.

Protocol version 1

Evaluating plantar foot pressure in a novel diabetic offloading device

IRAS code 198005

Essential documents include (this list is not exhaustive):

- Signed informed consent documents for all subjects.
- Subject identification code list, screening log (if applicable) and enrolment log.
- Record of all communications between the Investigator, the REC and the Sponsor.
- Copies of case report forms and documentation of corrections for all subjects.
- Investigational product accountability records.
- All other source documents (subject medical records, hospital records, laboratory records, etc.).
- All other documents as listed in section 8 of the ICH E6 Guideline for Good Clinical Practice (Essential Documents for the Conduct of a Clinical Trial).

Normally, these records will be held in the Investigator's archives. If the Investigator is unable to meet this obligation, he or she must ask the Sponsor for permission to make alternative arrangements. Details of these arrangements should be documented.

8.5. Study suspension, termination and completion

Suspension or termination of the study may occur at any time for any reason, following discussion between the Investigator and the Sponsor. Upon study completion, the Investigator will provide the Sponsor with final reports and summaries as required by regulations, and will be responsible for completing a premature end of study report to the Research Ethics Committee (REC) within 15 days.

9. DATA EVALUATION

9.1. Responsibilities

The principal investigator will be the sole responsible person as part of the Master of Science qualification will perform all tasks in collecting, storing, analysing and reporting the data for the research.

9.2. Hypotheses

Using the novel PulseFlow DF boot is as effective as usual standard care in off loading diabetic plantar forefoot ulcers.

9.3. General statistical considerations

In general, summary statistics (number of available measurements), arithmetic mean, standard deviation, median, minimum and maximum for quantitative variables and absolute and relative frequency tables for qualitative data will be presented.

9.4. Planned analyses

All data will be explored to check for assumptions of normality and homogeneity of variance for each variable, and to assess which statistical tests i.e. parametric or non-parametric test will be more appropriate to explore the data. The assumption of normality will be assessed graphically by histogram, box-plots and confirmed by statistical testing of significance of skewness and kurtosis. The spread, homogeneity and type of data will determine the type of statistical test. The paired t Test is predicted to be the statistical test of choice following statistician advice. This may change due to abnormal distribution of data once collection is complete.

Gait data will be checked for corruption or incomplete results associated with data capture or software error and rectified where possible either at the point of data collection or data analysis.

Exploratory statistical analyses will be performed to identify any potential associations between gait kinematics, clinical data and patient-reported outcomes. We will also explore the data for unexpected findings, including influential outliers, multicollinearity, truncation and missing data.

The primary outcome (section 2.2) will then be compared for systematic differences between the usual standard care and the PulseFlow DF boot using statistical tests based on the assumptions tested previously.

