5. STUDY DESIGN

5.1. *Study description*

Observational proof of concept study comparing the ability to redistribute forefoot pressure using a new foot offloading device compared to usual standard care.

The sample will be purposively selected taken from a local population of active diabetic foot ulcer patients. The measurements will be taken from patients wearing usual standard of care, sham shoe (closest to barefoot or baseline pressures) and the PulseFlow DF boot. The measurements from each patient will be collated to compute pti averages for the comparison.

5.2. *Study duration*

Approximately four months or time to complete required maximum sample size of 36 or ending 1st July whichever arrives first.

5.3. *Rationale for study design*

The issue of a novel boot should not influence clinical practice or further research until data is produced to support it.

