6.5.3. Randomisation process

Due to the type of study design patients can not be randomised. However the process of measuring usual standard of care, standard shoe and PulsFlow DF can be randomised. This will be performed by using a Latin 3x3 square design below which will be randomly allocated from a computer programme at the appointment time of measuring the foot pressures.

Protocol version 1**Evaluating plantar foot pressure in a novel diabetic offloading device****IRAS code 198005**

Sequence 1	Usual standard care	PulseFlow DF Boot	Standard shoe
Sequence 2	B PulseFlow DF Boot	Standard shoe	Usual standard care
Sequence 3	Standard shoe	Usual standard care	PulseFlow DF Boot

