6.5.6. Definition for the end of the trial

Numbers completed to the original sample size of 36 or more or by 1st July 2017.

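### Section 9.4 lets post-collection checks on each variable choose the primary test, and the randomised device order is not used in the analysis (minor)

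*Combined protocol and SAP*

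**What the plan says.** Section 9.4 opens with a general check: "All data will be explored to check for assumptions of normality and homogeneity of variance for each variable". Normality is to be judged from graphs and from significance tests of skewness and kurtosis. Then: "The spread, homogeneity and type of data will determine the type of statistical test". The expected method is given as a forecast: "The paired t Test is predicted to be the statistical test of choice following statistician advice", followed by "This may change due to abnormal distribution of data once collection is complete". The section closes by comparing the primary outcome between usual care and the boot "using statistical tests based on the assumptions tested previously". It gives no threshold, no replacement test and no mention of the within-patient difference as the quantity to examine.

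Section 6.5.3 sets out a 3x3 Latin square of three device sequences, "randomly allocated from a computer programme at the appointment time". It states no blocking or allocation ratio. Neither section 9.4 nor any other analysis text refers to order, period or sequence.

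Fewer than 36 patients may be measured. Section 5.2 gives a "required maximum sample size of 36 or ending 1st July whichever arrives first", and section 6.5.6 ends the study at "Numbers completed to the original sample size of 36 or more or by 1st July 2017". Section 6.2 says the study is meant to inform the size of later studies.

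**The concern.** There are two separate matters.

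**Test choice.** Every patient is measured in both devices, so the primary comparison depends only on the within-patient differences. It does not require each device's values to be normal, nor equal spread in the two devices. As worded, the plan can leave the paired t test because of features that do not bear on it. If spread is used, the choice can depend on the effect itself, since a boot that scales PTI down also scales its variance down. A switch to a rank test also changes what is estimated, after the data have been seen. Under section 9.1 one person collects, analyses and reports the data, so advance specification is the main safeguard.

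**Device order.** If PTI drifts over the visit, the drift enters each patient's difference according to sequence. An analysis that ignores sequence leaves it in the error term. The interval is then wider than it need be, and the SD of the differences, which later sample sizes would use, is too large.

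**Working it through.** **The plan's own figure.** Section 6.2: 12 per group x 3 = 36, as stated. The documents give no PTI variance, alpha, effect size or period effect. All inputs below are therefore assumptions: two-sided 5% tests, with effects in SDs of the within-patient difference. Results for test choice are simulated at n=36.

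**1. Does the switch change the target?** Take shifted log-normal differences with true mean zero and log-SD s. Their skewness is (e^(s²)+2)·√(e^(s²)−1), which is 1.75 for s=0.5 and 3.3 for s=0.75. The skewness and kurtosis tests are applied to the differences themselves.

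| | Skewness 1.75 | Skewness 3.3 |
|---|---|---|
| Differences flagged | 79% | 95% |
| Rejection, switch to signed-rank if flagged | 13% | 23% |
| Rejection, always signed-rank | 13% | 23% |
| Rejection, fixed paired t | 6-7% | about 8% |
| Distance of signed-rank target from mean | 0.12 SD | 0.17 SD |

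The excess comes from the different target. Moving the check from each device to the differences does not remove it.

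**2. Cost when the differences are normal.** With skewed patient levels, normal differences and a true difference of 0.5 SD, power is about 82% when the test switches on a flag in either device, and about 83% for the fixed t test. Type I error is about 5% for both.

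**3. How often do per-device checks mislead?** This depends on the model (patient levels log-normal, log-SD 0.3 to 0.6; formal tests only).
- Differences normal and unrelated to level: a flag on either device in 51-88% of studies, on the differences in 8-9%.
- Boot scales PTI by 0.6 to 0.8, with multiplicative noise of log-SD 0.1 to 0.3: about 60-96% against 28-89%.

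**4. Homogeneity.** Take bivariate normal data with a coefficient of variation of 30%, so the differences are exactly normal, and a median-centred Levene test. The plan names no homogeneity test, so Levene is an assumption.

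| Correlation between devices | Scale 0.8 | Scale 0.7 | Scale 0.6 |
|---|---|---|---|
| 0.955 | 2% | 39% | 95% |
| 0.5 | 16% | 44% | 78% |

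**5. Device order.** In the printed sequences the boot position minus the usual-care position is 2−1=+1, 1−3=−2 and 3−2=+1. The mean is 0 and the variance (1+4+1)/3 = 2. With a linear step of d SDs per position and 12 patients per sequence, the drift cancels from the mean, and the SE and SD are multiplied by √(1+2d²·36/35):
- d=0.1: √1.0206 = 1.010
- d=0.25: √1.1286 = 1.062
- d=0.5: √1.5143 = 1.231, which means a full SD between first and third position; nothing in the documents suggests a drift that large.

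**6. Cost of adjusting for sequence when there is no period effect.** Ratio of adjusted to unadjusted interval width, with n−3 degrees of freedom for the adjusted analysis:

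| n | Balanced | Simple allocation | Break-even d, simple allocation |
|---|---|---|---|
| 36 | 1.002 | 1.034 | 0.19 |
| 24 | 1.004 | 1.055 | 0.24 |
| 18 | 1.008 | 1.081 | 0.29 |
| 12 | 1.023 | 1.134 | 0.38 |

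The break-even is √((ratio²−1)/2); at n=36, √((1.034²−1)/2) = 0.19. Under simple allocation at n=12 a sequence is empty in about 3·(2/3)^12 = 2.3% of studies; these were redrawn.

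**The case against.** This is an exploratory, single-visit proof-of-concept study with a named default test, expected on statistician advice. The only explicit reason for leaving that test is an abnormal distribution. The opening sentence of 9.4 also serves the exploratory associations, and a reference to each variable does not exclude a derived difference. A non-parametric alternative to a paired t test leaves few candidates. Section 9.3 already commits to reporting the mean, SD and median. For device order, the Latin square deals with it by design. Section 7.2.1.1 adds familiarisation, 30 minutes of acclimatisation to the boot, and measurement only once the patient walks without balance support. Section 7.2.1.2 puts the measurements for all three devices at 10 to 15 minutes.

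Most of this stands, and it limits the size of the point. It does not remove it: 9.4 says that spread and homogeneity determine the test, and its last sentence carries the earlier checks into the primary comparison.

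Three stronger readings are tempting, and the documents support none of them.
- A reader might infer that pre-testing makes the primary analysis invalid. With normal differences, type I error stays near 5%. The 13% and 23% need strong skewness that the documents do not report, and they reflect the signed-rank test's own target.
- A reader might infer that per-device checks will nearly always discard a sound t test. The 51-88% against 8-9% contrast needs differences unrelated to level. If the boot scales PTI, the gap can be small.
- A reader might infer that ignoring order biases the comparison. Under balanced sequences a period effect cancels. Under simple random allocation, chance imbalance can shift a single estimate (a 14/9/13 split gives (14−18+13)/36 = +0.25 of the step), but it does so in either direction, and the paired t test stays valid.

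**Conclusion.** The point holds as a minor one. The primary test is left to checks made after data collection. One of those, homogeneity between devices, is not an assumption of the comparison, and no alternative is named. The harm that matters is a change from a mean difference to a rank-based location. It is negligible if the differences are near normal and material only if they are strongly skewed. The remedy is therefore to fix the analysis, since relocating the check leaves the same change of target.

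The unused device order is a possible loss of precision: 1% or 6% in the SE and in the reported SD for an assumed step of 0.1 or 0.25 SD under balance. Given the acclimatisation and the short measurement time, it may be near zero. Every magnitude here rests on assumed distributions, correlations and period steps, because the documents give none.

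**What to change.** In section 9.4:
- State the primary analysis in advance as the mean within-patient boot-minus-usual-care PTI difference with its confidence interval, not switched on assumption checks.
- Delete spread and homogeneity as determinants of the test for this comparison. Per-variable checks may stay for the exploratory associations.
- Inspect the differences or residuals for description only, and name the Wilcoxon signed-rank test as a sensitivity analysis.
- Adjust the difference for randomised sequence (the equally weighted mean of the three sequence-specific mean differences), with the unadjusted paired t test as a sensitivity analysis. Report the SD of the differences with and without sequence removed.

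In section 6.5.3, allocate the three sequences in balanced blocks.

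This takes a few sentences in 9.4 and one in 6.5.3. If there is no period effect, the adjustment widens the interval by about 0.2% at n=36 and 2.3% at n=12 when sequences are balanced. Without blocking the cost is about 3% to 13% over the same range, so the adjustment should be adopted only together with blocking. That matters because recruitment may stop short of 36.
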